8.5.4 Efficacy Analyses

Not applicable.

8.5.5 Analysis of Further Endpoints

Not applicable.

8.6 Interim Analysis

All the analyses described above (primary and secondary safety endpoints) for the 10-year final analysis will also be performed at 5 years after cessation of r-hGH treatment.

The 5-year interim analysis will be performed when 200 subjects enrolled in the study will have completed the 5-year study period after discontinuation of r-hGH treatment, and will include the available clinical data from 5 years after discontinuation of r-hGH treatment.

Further details will be provided in the SAP.

8.7 Imputation of missing data

Imputation of missing data will be performed for the analyses performed at the 5- and 10-year time points. An example is given as follows:

- If a subject experienced an event after 3 years and then dropped-out at 4 years, then this subject will be incorporated into the 5- and 10-year analyses as having had the event.
- If a subject dropped-out at a given time *t* without having experienced an event, this subject will not be included in subsequent analyses (after time t).

This imputation of missing data will not be applied to analyses of "subject-years".

9 Ethical and Regulatory Aspects

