8.1 Sample Size

It has been agreed with the Health Authorities to organize an observational study to have followup data on a minimum of 200 subjects born SGA for 10 years after cessation of Saizen® or other r-hGH therapies.

It has been estimated that up to 35% of subjects are likely to be lost or will drop out during the 10-year study duration (which can be due to withdrawal of consent, lost to follow-up, or death). Therefore, it was decided to recruit approximately 300 subjects in the SALTO study to have the 200 subjects for the final analysis at 10 years of follow-up. The sample size of 300 subjects represents 150% of the 200 subjects completing the study, as requested by the Health Authorities.

While recruitment is still open, the Sponsor will closely monitor the subject dropout rate to determine the need to recruit additional subjects. If the attrition rate is anticipated to be greater than 35%, additional subjects may be recruited to maximize the probability that 200 patients will have completed the study.

Figure 2 Determination of planned sample size.

^{*}Discontinuation includes: Lost to FU, protocol deviation, non-compliance, AEs, patient decision and other reasons.

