8.3 Endpoints

8.3.1 Primary Endpoints

The number and proportion of subjects diagnosed at any time during the 10-year follow-up will be tabulated for the two primary endpoints:

- Type 2 diabetes mellitus
- Any malignancy

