8.4 Analysis Sets

The **safety population** will be defined as all subjects having been included in the present study and have received r-hGH at least once for treatment of short stature due to SGA.

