8.5.2 Analysis of Primary Safety Endpoints

For primary endpoints, details for each subject of the safety population will be listed and will include at least; time on follow-up, onset date(s) of event(s) and description of event(s).

In parallel with numbers and proportions of subjects experiencing the events, the incidence rate per subject-years of follow-up will be calculated during the 10-year follow-up. The subject-time of follow-up will be defined as the time between the day of last r-hGH treatment and the end of the 10-year period. Furthermore, an analysis of association of the primary endpoints with subject characteristics (e.g., age, sex, blood pressure, BMI, family history) and possible confounding factors of the diseases (e.g., concomitant treatment, medical history, environmental factors) will be conducted. Exploratory analysis will be performed by each brand of r-hGH product if permitted by sample size per brand.

Further details will be provided in the SAP.

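### Section 8.7 keeps drop-outs who had an event and removes those who had none, so the 5- and 10-year proportions for both primary endpoints are biased upward if drop-out is independent of outcome

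*Protocol*

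**What the plan says.** The protocol reports each primary endpoint (type 2 diabetes mellitus; any malignancy) in two ways. Section 8.3.1: "The number and proportion of subjects diagnosed at any time during the 10-year follow-up will be tabulated". Section 8.5.2 adds that "the incidence rate per subject-years of follow-up will be calculated during the 10-year follow-up". Section 8.6 repeats all the analyses at 5 years after cessation.

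Section 8.7 sets the handling of drop-outs through two bullets, introduced as an example:

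- Event at 3 years, drop-out at 4 years: "then this subject will be incorporated into the 5- and 10-year analyses as having had the event".
- Drop-out at time t without an event: "this subject will not be included in subsequent analyses (after time t").

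The section closes by exempting the subject-years analyses from this rule.

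Section 8.4 defines the only analysis set, the safety population, as "all subjects having been included in the present study and have received r-hGH at least once" for short stature due to SGA. It makes no exclusion for drop-out.

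On the amount of loss, section 8.1 states: "It has been estimated that up to 35% of subjects are likely to be lost or will drop out during the" ten years of the study. Death counts towards that figure.

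**The concern.** Consider two subjects who leave on the same day in year 4, one with a diabetes diagnosis in year 3 and one without. At years 5 and 10 the first is counted in numerator and denominator, and the second in neither. Whether a drop-out counts is decided by the outcome being estimated. Section 8.7 calls this imputation, but nothing is imputed: it is an outcome-dependent exclusion.

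No significance test and no control group are planned, so these estimates are the study's main product, delivered under a post-approval safety commitment. The distortion does not shrink as the sample grows. It would also appear at the interim, for every subject who has left by year 5.

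The rule sits uneasily with section 8.4 as well. The defined population keeps every drop-out, while the proportions would be computed on a subset of it.

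**Working it through.** **The plan's own figure.** Section 8.1 wants 200 completers with up to 35% loss. 200 / 0.65 = 307.7, so 308, close to the stated figure of approximately 300. Conversely, 300 × 0.65 = 195, and 200 of 300 implies 1 − 200/300 = 33.3% loss.

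**Inputs.** Loss over 10 years: up to 35% (section 8.1). Entry: from the day after the last dose to 5 years after cessation (section 5.1). The protocol gives no event risk, no timing of drop-out, no 5-year loss and no distribution of entry times. These are assumptions below, and they are varied.

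**Direction under independent drop-out.** Let F(τ) be the true risk by time τ, f its density, S = 1 − F, and G(t) the probability of still being in the study at t. Section 8.7 estimates A/(A + B), where

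- A = ∫₀^τ f(t) G(t) dt (event before drop-out and before τ)
- B = S(τ) G(τ) (event-free and still in the study at τ)

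G never increases, so A ≥ F(τ) G(τ). Hence A/(A + B) ≥ F(τ). Equality needs no drop-out before τ among those at risk. At 5 years that would be so if every subject entered at year 5.

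**Illustration.** Constant hazards, entry at cessation, 35% loss, assumed 10-year risk 2%.

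- Drop-out hazard d = −ln(0.65)/10 = 0.04308; event hazard h = −ln(0.98)/10 = 0.00202
- h/(h + d) = 0.00202/0.04510 = 0.0448
- 10 years: B = 0.98 × 0.65 = 0.637; A = 0.0448 × (1 − 0.637) = 0.0163. Proportion = 0.0163/(0.0163 + 0.637) = 2.49%, against a true 2.00% (+24.5%)
- 5 years: B = √0.637 = 0.798; A = 0.0448 × (1 − 0.798) = 0.0090. Proportion = 1.12%, against a true 1.01% (+11.5%)

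| Assumed 10-year risk | Loss at 10 years | Reported at 10 years | Relative bias, 5 years | Relative bias, 10 years |
|---|---|---|---|---|
| 1% | 35% | 1.25% | +11.5% | +24.7% |
| 2% | 35% | 2.49% | +11.5% | +24.5% |
| 5% | 35% | 6.18% | +11.3% | +23.7% |
| 10% | 35% | 12.24% | +11.0% | +22.4% |
| 2% | 33.3% | 2.46% | +10.8% | +22.8% |
| 2% | 20% | 2.24% | +5.7% | +11.8% |
| 2% | 10% | 2.11% | +2.7% | +5.4% |

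**Sensitivity to timing** (2% risk, 35% loss; drop-out constant, uniform, early or late; event hazard constant or rising; entry at 0, 2.5 or 5 years, with the 35% falling between entry and year 10). The relative bias ranges from 0% to +18% at 5 years, with zero when all enter at year 5, and from +9% to +43% at 10 years. It was never negative.

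**Dividing by everyone enrolled is no remedy.** That gives A/F = 0.0163/0.02, about −19% at 10 years and about −10% at 5 years, because it treats every lost subject as event-free.

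**The case against.** The strongest case on the other side has four parts.

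*The bullets are only an example, and detail is left to the SAP.* They are nevertheless the only rule given, and the second is worded for any time t. A SAP that follows the protocol would inherit it. The point is not missing detail but a rule already fixed.

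*The error is small beside the sampling error.* This is true. At 2% risk the plan would see about 300 × 0.0163 = 5 events among about 196 counted subjects. For 5/200 the exact 95% interval is roughly 0.8% to 5.7%, about ten times as wide as the 0.5-point error. Under independent drop-out the error also overstates risk, so it would not hide a signal. This limits the consequence but does not make the rule correct.

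*The direction is not guaranteed.* This also stands. Section 8.1 counts death as loss, and the note to its Figure 2 lists adverse events among the reasons for discontinuation. Some loss may therefore be related to health.

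*Nothing is irretrievable.* Follow-up time and onset dates are listed for each subject (section 8.5.2), so another estimator can be computed later. That makes the fix cheap; it does not remove the need for it.

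A reader might also infer more than the protocol supports:

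- That 11% and 24% are fixed results. They are relative figures from one scenario; section 8.1 gives 35% only as an upper planning value.
- That event-free drop-outs lose all their observed time. They are removed only from analyses after they leave, so someone leaving in year 7 still counts at year 5. The subject-years rate is exempt.
- That section 8.5.2 contradicts the rule. Its reference to the safety population concerns a listing, not a denominator.
- That the proportion and the incidence rate are biased in opposite directions. That depends on a literal reading of the subject-time definition in section 8.5.2, which is a separate matter and does not follow from section 8.7.

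**Conclusion.** Section 8.7 is wrong as written. Under drop-out independent of outcome, the 5- and 10-year proportions for both primary endpoints are biased upward, with the single exception of no bias at 5 years if all subjects enter at year 5. With 35% constant loss, entry at cessation and an assumed 10-year risk of 1% to 10%, the relative bias is about +11% at 5 years and +22% to +25% at 10 years. The absolute error at 2% risk is about half a percentage point at 10 years. The bias falls roughly in step with the loss.

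The existence and direction of the bias rest on independence alone. Its size rests on event risk, timing of drop-out and timing of entry, none of which the protocol gives. If drop-out depends on health, the net direction cannot be settled from the document. The tension with section 8.4 is real, but it calls for clarification and is not a flat contradiction.

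**What to change.** Delete the two bullets in section 8.7. In their place:

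- Estimate 5- and 10-year cumulative incidence of each primary endpoint in the whole safety population, as 1 minus Kaplan-Meier or, with death as a competing event, by Aalen-Johansen.
- Censor event-free subjects at last contact with known status.
- Report pointwise 95% confidence intervals.
- Keep the raw count n/N as description only.
- Apply the same method at the 5-year interim.

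Under independent drop-out this removes the bias described here. It does not cure loss that depends on health, so that assumption should be stated with the result.

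The cost is protocol and SAP wording plus standard survival code. No new data are needed: onset dates and time on follow-up are already to be listed for each subject.

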9.1 Responsibilities of the Investigator

Investigators are responsible for screening and enrolling subjects into the study, for informing subjects of study process, for collecting subjects' demographic and medical data, for contacting the treating physician/GP when medical data is available, for following-up with the subjects at year 5 and 10 as well as for entering the relevant information into the eCRF for each subject.

Investigators will enrol subjects who have received Saizen® or other r-hGH products for the treatment of short stature due to SGA, as part of clinical studies or the post-marketing setting. Furthermore, Investigators will be encouraged to inform subjects who are still under r-hGH treatment about the EMR 200098 008/ SALTO study.

Even though patients will sign an ICF and enter into the study once r-hGH therapy is completed or permanently discontinued, the investigator will ask the subjects to provide a CICF while still on therapy, in order to allow the CRO's PMC to contact the subject and track subject contact information. The signature of the CICF is optional and will not limit the patient's participation in the SALTO study once eligibility criteria are met (see section 9.2).

As soon as the subjects complete or permanently discontinue treatment with Saizen® or other r-hGH products, the Investigators will be able to invite the subjects to participate in this observational study. At Sponsor's request he/she should obtain the written informed consent from the subject if he/she is an adult and also from the two parents or the legal guardian if he/she is minor. When minors reach the legal age, the Investigator will request written informed consent again. The Investigators will ensure that the subject's ICF will not be signed before these subjects have completed or have permanently discontinued or withdraw from r-hGH treatment (see also section 9.2).

Investigators will be also encouraged to re-contact or call back patients from their clinic who have permanently discontinued r-hGH treatment within a maximum of 5 years previously, in order to obtain consent to be enrolled into the study.

During the course of the SALTO study, subjects may no longer be required to visit their Investigator. Therefore, to ensure adequate collection of the post-treatment data, Investigators will obtain medical information through the subject's treating physician or GP. In addition, Investigators will contact subjects 5 and 10 years after discontinuation of r-hGH treatment to inform them of study development and to obtain any additional available relevant medical data for the study (see section 7.1).

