2. Malignancy risk: low birth weight has not been shown to be associated with increased risk of cancer in general, with the possible exceptions of testicular and renal cancer (4). A number of studies were retrieved in the published literature discussing the occurrence and/or recurrence of cancer or neoplasm during GH therapy. In one medium-sized and two large studies, GH therapy was not associated with an increase in the incidence of a first cancer compared to the general population.

However, GH treatment during childhood of survivors of cancer treatment has also been shown to increase slightly the relative risk of a second neoplasm (15), (16). Growth hormone therapy studied in two populations of cancer survivors, one with a control group, found an elevated risk of developing a secondary solid tumour in childhood cancer survivors treated with GH compared with non-treated survivors for one and a statistically significant raised frequency of colon cancer mortality after pituitary-derived GH treatment in another.

This observation is however disputed, given that other surveillance studies revealed no increase in observed cancer risk (17). The above results are based on a very small number of cases and may therefore require cautious interpretation.

There have been rare reports of brain tumours (de novo/recurrence) or leukaemia and extra-cranial solid tumour in subjects treated with Saizen® in the post-marketing surveillance period. From the currently available data, there is no evidence suggesting that Saizen® may increase the risk of cancers in treated subjects. It must also be noted that with an overall increase in subject-years of exposure, adverse events (AEs) which are related to commonly experienced medical conditions (as seen in the general population) tend to also be reported in the population treated with GH. However, no increase of reporting rates concerning neoplasms, both de novo and recurrence, was identified cumulatively since first marketing authorization of Saizen®.

4 Study Objectives

Primary objective of the study:

To assess the long-term safety of Saizen® or other r-hGH treatment for 10 years after cessation
of treatment, in terms of occurrence of type 2 diabetes mellitus and malignancies, in a minimum
of 200 subjects born SGA who received Saizen® or other r-hGH products for the treatment of
short stature

Secondary objectives of the study:

- To assess occurrence of metabolic syndrome
- To assess glucose metabolism parameters

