5.1 Overall Study Design and Plan

This study is a prospective and retrospective, single-cohort, multicentre, observational long-term post-approval commitment study in subjects born SGA, with no specific age restrictions, who received Saizen® or other r-hGH products for the treatment of short stature. It is a multinational study that will be performed at up to approximately 40 to 60 sites globally. The study will consist of a 10-year post-treatment safety assessment in subjects who were previously treated with r-hGH and who completed or permanently discontinued r-hGH therapy. Eligible subjects may have been enrolled in sponsored clinical studies or may have received r-hGH products in a post-marketing setting. Subjects may be enrolled at any time from the day after their last r-hGH dose up until 5 years after treatment cessation. The maximum duration of follow-up will be 10 years after treatment cessation. All subjects must have received r-hGH products for the treatment of short stature due to SGA as approved per country product label. There is no control group.

The overall objective is to collect safety data with a primary focus on type 2 diabetes mellitus and malignancies during the 10-year follow-up period after termination of r-hGH treatment in the SGA subjects (see section 4).

The aim is to have a final study population of 200 subjects after 10 years of follow-up for analysis. Approximately 300 subjects will be enrolled at study initiation in order to compensate for anticipated loss to follow-up (see section 8.1).

All subjects must sign the Informed Consent Form (ICF) to be enrolled in the study. Subjects may sign the ICF on the day after r-hGH treatment discontinuation (see section 9.2) and up to 5 years after treatment cessation. Prior to enrolment into the study, subjects who are currently being treated with an r-hGH product may be asked to optionally sign a Contact Information Consent Form (CICF) in order to allow the CRO's PMC to contact the subjects and track subject contact information only (see section 9.2).

Because SALTO is a post-treatment observational study, no scheduled study-specific visits, assessments or interventions are scheduled during the study (see section 7.1).

[figure not shown]

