- After every yearly call from the PMC, the PMC will update the contact information of the subject and subject's treating physician in the appropriate databases, and send the "Yearly Subject SALTO kit" to the subject/contact person. In addition, the PMC will identify any relevant change on the subject's health status, and will contact the Investigator who will obtain the relevant medical data from the subject's treating physician as previously described.
- 2. The subject can request a copy of his/her medical history/laboratory results from the treating physician/GP and send it to the Investigator who will enter the information into the electronic case report form (eCRF).
- 3. The Investigator will call the subject 5 and 10 years after r-hGH discontinuation to obtain any additional available relevant medical information.

Data collection will start once subjects have entered the study and will continue for a maximum of 10 years after discontinuation of treatment with Saizen® or other r-hGH products. Prior to collecting any data, the Investigator (i.e. paediatrician/endocrinologist) will ensure that the subject has provided a signed, written ICF according to the procedure described in section 9.2.

For subjects who have entered the study within the 5-year period after r-hGH treatment discontinuation, any data of interest occurring from the time of permanent cessation of r-hGH therapy up to the signature of the ICF will be retrospectively collected and recorded into the eCRF by the Investigator.

Data reporting is allowed at any time if a subject or his/her Investigator reports an adverse event related to changes in glucose metabolism parameters or to malignancy or to any Serious Adverse Event related to r-hGH treatment.

During subsequent follow-up visits, the Investigator or subject's treating physician/GP (when applicable) will ensure that the subject is informed and updated on the study.

Method of Reporting AEs of Interest

At the time of obtaining Informed Consent, the Investigator will explain the process of reporting an AE to the subject. The subject will be provided with a leaflet containing information on the AEs of interest (i.e., type 2 diabetes mellitus, metabolic syndrome and/or changes in glucose metabolism parameters, fasting insulin levels, HbA_{1c}, 2-hour OGTT results, blood pressure, lipid parameters, and parameters related to malignancies) and key message/information of the Company's post-approval commitment (PAC).

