7.4.1.3 Definition of the Adverse Event Reporting Period

The AE reporting period for safety surveillance is defined as the 10-year period after cessation of r-hGH treatment (i.e., during the 10 years after the date of last r-hGH administration).

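### Call-back of patients who stopped r-hGH up to 5 years earlier is left to the investigator's choice, although their pre-consent events count in the primary incidences

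*Protocol*

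**What the plan says.** Section 9.1 makes the site the gatekeeper: "Investigators are responsible for screening and enrolling subjects into the study". Section 2 and section 7.1 describe these investigators as the paediatricians or endocrinologists who treat such children at their clinics.

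For patients who have already stopped, section 9.1 says "Investigators will be also encouraged to re-contact or call back patients from their clinic who have permanently discontinued r-hGH treatment", within a limit of 5 years. For patients who are just stopping, it says that "the Investigators will be able to invite the subjects to participate in this observational study" as soon as treatment ends.

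On timing, section 5.1 states: "Subjects may be enrolled at any time from the day after their last r-hGH dose up until 5 years after treatment cessation". For those entering late, section 7.1 has the investigator record retrospectively "any data of interest occurring from the time of permanent cessation of r-hGH therapy up to the signature of the ICF". Section 7.4.1.3 states: "The AE reporting period for safety surveillance is defined as the 10-year period after cessation of r-hGH treatment". Section 8.3.1 then states: "The number and proportion of subjects diagnosed at any time during the 10-year follow-up will be tabulated for the two primary endpoints". Section 8.5.2 likewise starts subject-time at the last r-hGH treatment, and section 5.1 says that there is no control group.

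**The concern.** A patient called back three or four years after stopping may already have a primary event, or be known to be free of one. That outcome will count. The person who decides whether to make the call may know it, and the protocol asks for the call without requiring it. Entry can then depend on the outcome.

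The bias could run either way. A patient with a glucose problem who still attends the endocrine clinic may be easier to recruit. A patient treated elsewhere for cancer may be passed over.

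The stated objective is "To assess the long-term safety of Saizen® or other r-hGH treatment for 10 years after cessation", and the result is an uncontrolled incidence. Nothing inside the study would reveal the distortion, and without counts of eligible and invited patients a reader could not judge it from outside. An SAP cannot repair this, because it cannot recover numbers that sites never recorded.

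**Working it through.** **1. The protocol's own figure.** Section 8.1 plans about 300 subjects for 200 completers with up to 35% attrition. 200 / (1 − 0.35) = 308, 200 × 1.5 = 300, and 300 × 0.65 = 195, so the approximate figure of 300 is reproduced. It does not bear on selection. It serves below only to convert risks into expected events. The protocol gives no expected event rate.

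**2. Can a pre-consent event count?** Yes, on a plain reading. Section 7.1 collects it, section 7.4.1.3 puts it in the reporting period, section 8.3.1 counts any diagnosis in the 10 years, and section 8.5.2 counts the matching subject-time. The criteria in 5.3.1 and 5.3.2 do not mention diabetes or malignancy that arose after cessation. One sentence in 7.4.1.1 excludes unchanged conditions present at study start from being adverse events. If study start means enrolment, that conflicts with 7.1 and 7.4.1.3, and the passages need to be reconciled.

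**3. Is invitation of past patients complete?** Not by any rule we can see. Section 5.3 describes the population as any qualifying subject, but that defines eligibility and does not say who is approached. Section 5.3.4.1 collects reasons for withdrawal and section 8.1 monitors dropout. Nothing similar covers entry.

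**4. Illustration.** All three inputs are assumptions:
- p: true 10-year risk
- f: share of those events already present and known at entry
- k: chance that such a known case is enrolled, relative to everyone else

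Observed risk = [k·p·f + p·(1 − f)] / [k·p·f + 1 − p·f]

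For p = 2% and f = 50%:
- k = 0.5: (0.005 + 0.010) / (0.005 + 0.990) = 0.015 / 0.995 = 1.51%
- k = 1: 0.020 / 1.000 = 2.00%
- k = 2: (0.020 + 0.010) / (0.020 + 0.990) = 0.030 / 1.010 = 2.97%

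| p | f | k = 0.5 | k = 1 | k = 2 | expected events in 200 (k = 0.5 / 1 / 2) |
|---|---|---|---|---|---|
| 2% | 50% | 1.51% | 2.00% | 2.97% | 3.0 / 4.0 / 5.9 |
| 2% | 25% | 1.75% | 2.00% | 2.49% | 3.5 / 4.0 / 5.0 |
| 1% | 50% | 0.75% | 1.00% | 1.49% | 1.5 / 2.0 / 3.0 |
| 1% | 25% | 0.88% | 1.00% | 1.25% | 1.8 / 2.0 / 2.5 |

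**5. How large can f be?** If events fell evenly over the 10 years, a subject enrolled L years after stopping would have f = L/10 at most. The 5-year limit gives 5/10 = 50%, and a gap of 2.5 years gives 25%. A patient enrolled the day after the last dose has f close to 0. So f = 50% describes call-back at the limit with every event known to the investigator, and a mixed cohort would sit lower. With k = 1 the observed risk equals p, which is what complete invitation aims at, provided consent is equally likely with and without an event.

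**The case against.** Several objections carry weight.

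- **New stoppers.** A reader might infer that the sentence on inviting patients at the end of treatment also gives investigators a free choice. It mainly fixes the earliest moment for invitation, and the same paragraph bars consent before treatment ends. Section 9.1 also has contact-detail consent sought while patients are still on therapy, before any post-treatment outcome exists. The point is therefore confined to call-backs.
- **Knowledge of outcomes.** The protocol does not say that investigators know them. Follow-up data come through the GP or treating physician, and subjects need not visit the investigator. An investigator who has lost touch cannot select on an unknown outcome. This limits the effect but does not exclude it.
- **Few subjects per site.** 300/60 = 5 and 300/40 = 7.5, from which a reader might infer that discretion decides who is in the cohort. The documents give no number of eligible patients, so these figures fit near-complete enrolment of a small population equally well.
- **Records may exist.** The appendix item on recruitment is cut off in our copy, and the list of archived documents in section 10.3 is not exhaustive. A screening log may exist at sites. That would ease the fix, but it would not turn encouragement into a requirement.
- **Scope.** Section 8.5.1 speaks of incidence among study participants and plans no testing. Even so, a safety commitment is of little use if the participants may have been chosen by outcome.

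Selection on family history or other known risk could also carry into the years after consent. Its effect on future events would be partial, and it is not quantified here.

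**Conclusion.** The concern holds for patients called back after stopping. As written, the plan lets entry depend on an outcome that has already occurred and will be counted, with no control group and no visible count of those left out. Neither the direction nor the size can be derived from the documents. At an assumed 2% risk, with half of events known at entry and known cases enrolled half or twice as often, the result moves to about 1.5% or 3.0%. With a quarter known, it moves to about 1.75% or 2.5%.

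A reader might infer that the estimate could be halved or doubled. That follows only if k applies to every case, including those not yet arisen: at p = 2%, k·p/(k·p + 1 − p) gives 1.0% for k = 0.5 and 3.9% for k = 2. Investigators cannot recognise all future cases at invitation, so the documents do not support that reading.

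Sampling error is also large: 4 events in 200 have an exact 95% interval of 0.55% to 5.04%. The illustrated shifts lie inside it, but the interval does not allow for selection, and one or two cases selected in or out would change the point estimate noticeably.

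**What to change.** In section 9.1, replace the encouragement to re-contact with a requirement. Each site identifies from clinic records all SGA patients who stopped r-hGH and are still within the 5-year window, plus all later stoppers, and invites every one regardless of current health.

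Each site keeps aggregate, non-identifying counts only: eligible, invited, refused, not reachable or died, enrolled. A patient-level log of people who never consented would sit badly with section 9.2, which requires written consent before data collection starts, and at 5 to 8 subjects per site it could identify individuals.

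Report the counts with the primary results, and show events and subject-time before and after consent separately. Enrolment has run since 2011, so for patients already enrolled, give the counts where clinic records allow. Early stoppers now outside the window can no longer be invited.

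The cost is a wording change and modest site administration, with no added subjects, visits or tests. Refusal and death before call-back become visible but are not removed.
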